**Statistical Plan:**

**ClinicalTrials.gov Results Record 220939 (NCT02755818)**

IRB Number:	220939
Protocol Name:	CCRC: The Independent Effects of Level of Kidney Function and Body Composition on Establishing HDL Cholesterol levels
Principal Investigator Name, Email, Phone:	[name], PhD, [contact] [contact]
Primary Contact Name, Email, Phone:	[name], [contact] [contact]

**Subject:** Outcomes/Statistical Plan

HDL levels tend to be low in dialysis patients and triglyceride levels (TG) tend to be high. The levels of HDL are regulated in part by cholesterol ester transfer protein (CETP) and lecithin cholesterol ester transfer protein (LCAT) and TG levels by lipoprotein lipase (LPL). We have planned this study to establish the relationship between estimated glomerular filtration rate (eGFR) and the levels of LCAT, CETP and LPL and their association with HDL levels at different levels of eGFR. Patients with normal renal function with low HDL tend to have low CETP and high LCAT. Patients on dialysis by contrast have low LCAT. We have designed this study to establish the relationship between eGFR, the levels of these enzymes and both HDL and TG levels.

LCAT, CETP and LPL as a function of residual eGFR were to be analyzed by linear regression. This analysis was not done due to our inability to recruit willing patients with CKD3b and CKD4 within our recruitment criteria.

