DESCRIPTION OF STUDY

Principal Investigator: [name], PhD
Title of the Study: CCRC: "The independent effects of level of kidney function and body composition on establishing HDL cholesterol levels" (220939-7)

PURPOSE AND PROCEDURES:

1. Describe the study format and whether it is single or multi-center; industry-sponsored or investigator initiated; and the funding source.

This is a single center cross sectional analysis of body composition and lipoprotein level and structure among patients with graded levels of renal failure in comparison to control subjects. This is not a treatment or outcome trial.

2. Briefly describe the specific aims of the study, research methods and procedures.

To establish the relationship between HDL cholesterol and both body composition and insulin resistance measured as HOMA among a cohort of non diabetic non proteinuric patients with advanced CKD, (stage IIIb, Stage IV and stage V) compared to non diabetic subjects having normal kidney function (eGFR \geq 80 ml/min)

3. Address if therapeutically removed tissue will be collected, what types, and for what purposes.

N/A

4. Specify the nature, frequency and duration of tests, if any.

There is a potential for blood to be drawn two times. In patients who are under immediate care with recorded fasting blood sugar values in the non diabetic range (less than 120 mg/dL) obtained in the past 6 months, no blood samples will be obtained for screening and patients will be studied or excluded based upon laboratory values in either the UC Davis or DCI. The creatinine available in the medical record will also be used to establish the level of renal function. In patients in whom no recent evidence is available to exclude diabetes and for the valuation of baseline renal function, approximately 5 cc of blood will be obtained to measure a fasting blood sugar and serum creatinine. Patients with fasting blood sugar values equal to or greater than 120 mg/dL will be excluded. Dialysis patients have blood drawn at least monthly making only a single sample necessary for these patients. Subjects who are not on dialysis, i.e. normal control subjects and patients having chronic kidney disease may require two blood samples - one 5 ml sample (1 teaspoon) and one 45 ml (3 tablespoon) sample obtained.

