5. If blood samples will be collected, identify in what manner and the maximum amount that will be collected over any 6 week period (if subjects are co-enrolled in other research studies, the volume of blood from the other study should also be included):

venipuncture venous catheter arterial puncture arterial catheter cutaneous

6. Any additional procedures (noninvasive) involved in this study activity must be described.

Mass, lean tissue mass, and bone mineral content, using a Hologic Discovery W bone densitometer (Hologic, Bedford, Massachusetts) in accordance with standardized procedures recommended by the manufacturer. DXA measurements will be performed with the patient in the supine position, dressed in light clothing, and wearing no metal objects. Total body scanning time will be approximately 11 min, and the total x-ray radiation received by each patient will be approximately 0.4 mrem.

Whole body bioimpedance spectroscopy (BIS) measurements will be performed using two different devices: 1.) an ImpediMed (ImpediMed Limited., San Diego, CA); 2) the Xitron in all patients while patients are in the supine position at the CCRC. Dialysis patients will be studied on a non dialysis day. The areas for electrode attachment will be cleaned with alcohol. Two injecting electrodes for applying alternating current will be placed on

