9. Address the location and duration of the study including follow-up period.

The study will take about an hour and will be conducted at the CCRC located in the Cypress Building, [name].

10. Clarify how you plan to monitor data to ensure subject safety.

Labs with critical values are reported to [name] directly.

11. Address whether you have the appropriate resources (study personnel and facilities) to conduct this study.

We have requested funding for a half time clinical coordinator who will be dedicated to this study for 2 years. The PI and the co PI will each devote 5% effort to recruitment, safety monitoring and data analysis.

12. Describe the role of each key member of your study personnel.

- [name] --Physician/PI: write/collaborate on manuscript from data collected and oversees study
- Physician/Co-PI: consent/collaborate on manuscript from data collected and oversees study
- CRC/Lab Tech: enroll, consent, collect specimen(s) as well as run assays on specimen(s).

SUBJECT SELECTION:

1. Identify the subject population.

The study population will consist of 20 prevalent hemodialysis patients, 20 patients having an estimated glomerular filtration rate (eGFR) between 15 and 29 and 20 patients having an eGFR between 30 and 45. Thirty subjects having normal renal function (eGFR \geq 80 ml/min) will be studied. Patients must be non diabetic (FBS \leq 120 mg/dl, not taking oral contraceptives or hormone replacement therapy, not on steroids, not on HIV treatment regimen, not have a functioning renal transplant and not taking a lipid lowering agent at the time of the research study.

2. Address how subjects will be recruited: direct person to person solicitation, by telephone, letter, advertisement, press release, notices, other. Provide the text.

See attached recruitment flyer(s).

3. State from where subjects will be recruited, when and how many.

Patients will be recruited from the UC Davis chronic kidney disease clinics (Stage IIIb and Stage IV CKD, from the dialysis patient population at our 4 DCI dialysis clinics (University, Southgate, Madison, and Rancho Cordova, and if necessary from the DaVita dialysis units which we are affiliated. Normal subjects will be recruited through the and by posting notices at University of California Davis, and on the bulletin boards at the UC Davis main campus.

Will be recruiting from outside of UC Davis and DCI using IRB approved methods.

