4. Specify the age of the research subjects.

18-75 years old.

5. List all criteria for including and excluding subjects.

Inclusion: Subjects will be recruited who are between 18 and 75.

Inclusion criteria:

- Men and women - ages 18-75
- Self report of stable body weight during the past six months
- BMI 18-40 kg/m²
- Hemodialysis dependent for at least 3 months (prevalent ESRD cohort)
- eGFR \geq 15 \leq 44 ml/min (CKD cohort)
- eGFR \geq 80 ml/min (Control cohort)

Exclusion Criteria:

- Diabetes Mellitus (American Diabetes Association definition: fasting glucose $>$ 120 mg/dl)
- Evidence of liver-hepatitis B, or thyroid disorders
- HIV by medical history (HIV test will not be performed)
- Renal transplant recipient
- Oral contraceptive, hormone replacement therapy
- Systemic use of systemic or inhaled corticosteroids in the past month
- Contraindication to systemic anticoagulation (heparin administration is necessary to measure levels of LPL, HL).
- Hemoglobin $<$ 8.5 g/dl (anemia)
- Current, within 2 months use of any hypolipidemic or anti-diabetic agents.
- Any other condition that, in the opinion of the investigators, would put the subject at risk
- Patients treated with a fibric acid derivative or niacin in the past 4 weeks.
- Urinary protein excretion of greater than 0.5 grams per day.

Patients will be screened by collection of serum for fasting blood sugar, creatinine, and measurement of urine

6. If women and minorities are excluded, provide rationale for such exclusion.

N/A

7. Attach the translated documents for subjects whose primary language is not English.

N/A

SPECIAL/VULNERABLE POPULATION (if applicable):

Surrogate consent for participation in a research study should be employed only to the extent that it is consistent with the intent of the Common Rule (45 CFR 46, Subpart A) and all other federal and state laws and regulations pertaining to protecting human subjects participating in research. Carefully review the IRB Policy on *Surrogate Consent For Research* for compliance with all applicable laws, regulations, and conditions of this policy. Investigators are reminded that use of surrogate consent shall apply on a case-by-case basis within the protocol.

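### The only analysis specified in the available text regresses three enzymes on eGFR; it has no HDL or triglyceride response and no body composition or HOMA term, so it cannot answer the study's stated question

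*SAP*

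**What the plan says.** The protocol's title makes HDL cholesterol the quantity to be explained: "The independent effects of level of kidney function and body composition on establishing HDL cholesterol levels". Its specific aim (Purpose and Procedures, item 2) is "To establish the relationship between HDL cholesterol and both body composition and insulin resistance measured as HOMA", in non-diabetic patients with advanced CKD compared with subjects who have normal kidney function. No statistical model, test or adjustment set follows in the protocol.

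The SAP (Outcomes/Statistical Plan) restates the purpose around three proteins. It wants the relation of eGFR to LCAT, CETP and LPL, the association of these with HDL across levels of eGFR, and the relation of eGFR and the enzymes to both HDL and triglycerides. One method follows: "LCAT, CETP and LPL as a function of residual eGFR were to be analyzed by linear regression". The next sentence says the analysis was not done, because willing patients with CKD stages 3b and 4 could not be recruited under the study's criteria. In the available SAP text, body composition appears only in the protocol name, and HOMA does not appear.

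**The concern.** An aim about independent effects on HDL needs HDL as the response, with kidney function and body composition in the same model. The stated regression has different responses and a single predictor. A statistician who followed the plan to the letter, with every planned subject recruited, would finish with three enzyme-on-eGFR slopes and no estimate for the question in the title.

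What is at stake is whether any answer about HDL can be called pre-specified. With no stated model, the choice of body composition measure, covariates and form of the kidney-function term is left open until the data have been seen. The recruitment shortfall explains why the eGFR regression was dropped. It does not explain why the aims on HDL, body composition and HOMA have no method. Those could have been examined in whichever subjects were enrolled.

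**Working it through.** The documents give no figure to reproduce. The check sets each stated objective against the one stated method.

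| Objective | Where stated | Response and terms needed | Method in the available text |
|---|---|---|---|
| 1. Independent effects of kidney function and body composition on HDL | Protocol title; repeated as the protocol name in the SAP | HDL on kidney function and body composition jointly | None |
| 2. HDL in relation to body composition and HOMA | Protocol, Purpose and Procedures, item 2 | HDL on body composition and HOMA | None |
| 3. eGFR in relation to LCAT, CETP and LPL | SAP, Outcomes/Statistical Plan | Each enzyme on eGFR | Linear regression, reported as not done |
| 4. Enzymes in relation to HDL at different eGFR | Same | HDL with the enzymes, by eGFR | None |
| 5. eGFR and enzymes in relation to HDL and triglycerides | Same | HDL, and triglycerides, on eGFR and the enzymes | None |

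Count: 5 objectives, 1 with a method, 5 − 1 = 4 without. Objective 5 overlaps objectives 3 and 4, so the count shows the pattern and is not an exact score.

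**Could the stated regression serve the title aim indirectly?** Written out, it is

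enzyme = a + b × eGFR + error,

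fitted for each of LCAT, CETP and LPL. The title aim needs

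HDL = β0 + β1 × (kidney function) + β2 × (body composition) + covariates + error,

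with β1 and β2 as the independent effects. Body composition is absent from the first equation, so b carries no information on β2. HDL is absent too, so b cannot give β1 without a further enzyme-to-HDL model, and none is specified. The same holds with triglycerides as the response.

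**Is there another analysis in the protocol?** Item 6 intends to compare two bioimpedance devices, but it names no method and does not concern HDL. The Cole-Cole fit described there is a measurement step. Neither supplies the missing model.

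**Do the study procedures supply the variables?**
- Body composition: yes. DXA is planned ("Mass, lean tissue mass, and bone mineral content, using a Hologic Discovery W bone densitometer"; the sentence starts mid-phrase in the available text, so the full list of DXA measures cannot be seen). Bioimpedance is planned too.
- Kidney function: cohort is defined for everyone. The dialysis cohort is defined as "Hemodialysis dependent for at least 3 months (prevalent ESRD cohort", with no eGFR range. That does not show that residual eGFR was unavailable in these patients.
- HOMA: unclear. Fasting glucose is mentioned. No insulin assay is named, but no full assay list is given for the main blood sample ("one 45 ml (3 tablespoon) sample obtained"), so it cannot be said that insulin was not measured.

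**The case against.** The strongest reply is that the record is incomplete. Part of the SAP was removed before review, the protocol is an IRB form without a statistics section, and the SAP's regression sentence does not claim to describe the only planned analysis. A reader might infer that the study never had an HDL model. The documents do not support that; they show only that no such model is in the available text. This limits the claim but does not defeat it, because the one method that is stated still answers a different question from the title.

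A second reply is that the SAP text is a note written at the results stage, in the past tense, for a study the protocol describes thus: "This is not a treatment or outcome trial". On that view this is a reporting gap. Much of this stands. A reader might infer that a published estimate is biased; none can be on this account, since the regression was not run. But a cross-sectional study with an aim of independent effects still needs a model that can separate them.

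A third reply is that details of a remedy are matters of preference. That also stands in part. A cohort term is not the only acceptable form for kidney function, DXA is not the only planned body composition measure, and the SAP's enzyme objective does not call for body composition in the enzyme regressions.

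**Conclusion.** The point holds for the available text. The single specified analysis could not, even if run, estimate the independent effects of kidney function and body composition on HDL, the relation of HDL to body composition and HOMA, or the SAP's own HDL and triglyceride objectives. It should be fixed, because the stated analysis addresses a different question from the title. It is not evidence of a distorted result.

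The size is the count above: four of five objectives without a method, and the fifth with a method that was not applied. No numerical loss can be attached. The SAP gives no enrolment figures and the documents do not say how strongly kidney function and body composition are related, so precision or power figures would rest on assumptions and would not measure this defect.

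A reader might also infer that no patient with CKD 3b or 4 was enrolled and that only two cohorts remain. The SAP reports an inability to recruit willing patients; it does not say the number was zero.

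**What to change.** Specify a multivariable linear model of HDL, and a matching one of triglycerides, with:
- kidney function, as cohort, or as eGFR if it is available for all subjects;
- one named body composition measure that the study procedures already provide, entered jointly with kidney function;
- age and sex as covariates.

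Report each adjusted coefficient with a 95% CI. Add HOMA if insulin was measured; if not, state that the HOMA aim is not addressed. For the association between the enzymes and HDL, name a method or state that it is not addressed.

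Label any model added now as post hoc and exploratory. If only dialysis and control subjects are available, state that the model cannot describe graded kidney function.

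The cost is SAP wording and analysis code. The body composition measurements, age and sex need no new visit. The statistical downside is a wider interval for the kidney-function coefficient where kidney function overlaps with body composition. The documents do not allow that amount to be calculated, and any reduction in residual variance from the covariates would offset some of it.
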